- *Inclusion criterion:* All children (aged 12 months and older) presenting (since 1-1-2014: moment of diagnostic guideline standardization for pedEoE) with diagnosed pedEoE at UZ Leuven eliminating either hen's egg or cow's milk or both and in complete remission after their latest biopsy (no longer than 12 months earlier, but preferentially as short as possible after their latest biopsy) are eligible for the study. If the last biopsy has been performed more than 12 months earlier, a new gastro-duodenoscopy will be performed to verify remission and rule out e.g. active gastritis. If they are on PPI and/or local budesonide treatment, this should be stable for at least 3 months and will remain untouched during the entire study. We will include 18 pedEoE subjects in total.
- *Exclusion criteria:*
 - Children younger than 12 months
 - Children with active pedEoE
 - Children who refuse to adhere to the protocol
 - Children with associated IgE mediated hen's egg and/or cow's milk allergy with specific IgE antibody titers that predict active (baked egg and/or baked milk) food allergy with cut-off titers as used at the consultation of allergy (KLL). Those children will become eligible however if their titers decrease while the study is still open.

Study design:

Study subjects and study procedure

If inclusion criteria are met, after obtaining informed consent from the parents (and when old enough, assent from the children) 18 children will be included in this pilot pedEoE trial.

Children will be provoked in-house (UZ Leuven petit-cru), based on the written procedure available for heated egg (wheat or rice flour based) or cow's milk provocation. If on diet for both, parents and children will decide which allergen they will start with, but both food products will be introduced sequentially in time (this is after complete termination of the first food introduction). Afterwards, they will introduce heated egg by cake or 20' boiled cow's milk at least three times a week for 8 weeks (as for the TETI study (10)) and will return to the hospital for a gastroscopy with biopsies. EoE remission will be studied on 2X3 biopsies

(upper and lower esophagus) by eosinophil staining within the routine anatomopathological laboratory within our hospital.

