[figure not shown]
T-1 V0: screening visit: within SOC; informed consent and assent

Heat denaturation in PedEoE-pilot-version 5 July 2023

T0 V1: visit 1: step 1 in hospital provocation and biomarker

T8 V2: 8 weeks later visit 2: gastroscopy with biopsy and biomarker
V2T: telephone guidance discussing biopsy results (Go/no go V3; if no go: V8 and V9 termination visit)

T9 V3: visit 3: clinical examination and dietary advice step 2

T17 V4: 8 weeks later visit 4: gastroscopy with biopsy and biomarker
V4T: telephone guidance discussing biopsy results (Go/no go V5; if no go V8 and V9 termination visit)

T18 V5: visit 5: clinical examination and dietary advice step 3

T26 V6: 8 weeks later visit 6: gastroscopy with biopsy and biomarker
V6T: telephone guidance discussing biopsy results

T27 V7: visit 7: clinical examination and dietary advice step 4

T35 V8: 8 weeks later visit 8: gastroscopy with biopsy and biomarker
V8T: telephone guidance discussing biopsy results

T37 V9: visit 9: termination visit

T45 V10 optional: new biopsy after step 5 (unlimited, unheated egg or UHT milk)

After at least 6 weeks post V9 (or V10 if applicable), inclusion for the second food allergen can occur (cross-over).

Blood and esophagus biomarker study

IgG4 staining on the biopsies will be performed by prof [name]. Baseline blood (2X10 mL) will be obtained before the in-house provocation procedure and serum will be stored for specific IgG4 analysis later on. In parallel, PBMC will be isolated at the Allergy and Clinical

immunology Research Laboratory (LACI) and stimulated *in vitro* with heat denaturated proteins, as routinely performed within LACI. B (and plasma) cells will be stained by 4-laserflow cytometry (BD *Fortessa*). IgG4 production in supernatants will be studied by ELISA (specific IgG4 by Immunocap 100) and membrane bound IgG(4) (on biopsy material) by flow cytometry. This procedure will be repeated during each gastroscopy (when IV line is placed).

Parents will be offered a parking ticket for the visits in UZ Leuven and a lunch ticket during the day of the study visits with gastroscopy. After the study is finished, study participants (and their parents) will be offered a ticket for an attraction park (choice out of 4 parks).

Statistical analysis

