The study is part of a funded FWO-TBM project that will start in October 2023. We will start the inclusion of the study trial from July 2023 on using internal funding for the first inclusion when needed. We hypothesize that the majority of children will start with hen's egg introduction, given the fact that more recipes containing hen's egg are existing and might change the lives of parents and children drastically when allowed. We hence do not anticipate or intend equal distribution of hen's egg and cow's milk inclusion. If in all 18 children step 1 induces reoccurrence of the disease, the study will be stopped and no cross-over to the second food allergen will any longer be possible.

Data reporting will be mainly descriptive. No statistical testing is foreseen.

Data policy

Ethics and regulatory approvals

The Participating Site and Investigator will perform the Study fully in accordance with the terms of the Protocol, this Agreement including all its appendices and Applicable Laws and Regulations (as defined as follows: the current version of the World Medical Association's Declaration of Helsinki, the guidelines and guidance documents specifying Good Clinical Practice ("GCP") and guidelines of competent authorities; all applicable laws, rules and legislation in relation to clinical trials, use of human biological material, data protection and the processing of personal data, and patient's rights, including but not limited to the General Data Protection Regulation 2016/679 ("GDPR") and the Belgian law of 30 July 2018 on the protection of natural persons with regard to the processing of personal data). The Participating Site will ensure that the Investigator and all employees, agents, contractors and/or the

representatives involved in the performance of the Study (jointly "Staff") are properly trained and sufficiently qualified. The Participating Site shall provide Staff with all necessary documentation to allow the proper performance of the Study, which shall be conducted in compliance with the Protocol. The Participating Site shall be responsible to ensure that all work performed by Staff is done in compliance with the Protocol, this Agreement and all Applicable laws and Regulations. The Participating Site undertakes to impose on all employees, agents, contractors and/ or representatives the terms and conditions not less strict than those set out in this Agreement.

[Insurance/Indemnity](#)

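### A child can enter on a remission biopsy that predates a change in PPI or budesonide, and remission lost before V1 would then count as a step-1 failure

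*Protocol*

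**What the plan says.** All references are to the Protocol.

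- **Entry biopsy (Material and methods, Inclusion criterion).** The child must be in complete remission on the latest biopsy, which must be "no longer than 12 months earlier, but preferentially as short as possible after their latest biopsy". The shorter interval is a preference, not a limit. A fresh examination is required only beyond that limit: "If the last biopsy has been performed more than 12 months earlier, a new gastro-duodenoscopy will be performed to verify remission".
- **Background drugs (same criterion).** For PPI or local budesonide, "this should be stable for at least 3 months and will remain untouched during the entire study". Nothing links the start of the stable period to the date of the biopsy.
- **Exclusion criteria.** "Children with active pedEoE" are excluded, but no biopsy or timing is attached to this criterion.
- **Number of study visits.** The first intervention visit reads "T0 V1: visit 1: step 1 in hospital provocation and biomarker". The first on-study histology is "T8 V2: 8 weeks later visit 2: gastroscopy with biopsy and biomarker". No gastroscopy is listed at V0 or V1.
- **Study subjects and study procedure.** A child who loses remission at step 1 goes back to strict avoidance for at least 10 weeks and then has another gastroscopy. The stated use of that result is to decide whether a child avoiding both foods may start the second one.
- **Background, Option 1 (local corticosteroids).** Local practice allows a dose reduction to be discussed once a later biopsy confirms continued remission.

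**The concern.** The primary end-point counts children who stay in remission after 8 weeks of heated egg or milk. With no control group, each child's state at V1 is the only comparator, so the count means what it says only if the child was in remission when step 1 began.

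The two entry limits do not secure that for a child whose drugs changed between the biopsy and the 3-month stable period. The biopsy then shows remission on a regimen the child no longer takes. The protocol's own description of practice makes this plausible: a remission biopsy can be what prompts a dose reduction, and three months later the same biopsy can still qualify the child.

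If remission was lost before V1, the V2 biopsy cannot tell that from a loss caused by the food. The heated food would look worse than it is. A child avoiding only one food would also leave the study after the repeat gastroscopy, and so would contribute nothing to the later steps or to the secondary end-point on remission kept at step 1 but lost with less heated protein.

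**Working it through.** The protocol gives no figure to reproduce here: there is no power calculation and no relapse rate.

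**Timeline, from the inclusion criterion and the visit list**

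- Oldest qualifying biopsy: 12 months, about 52 weeks, before entry.
- Required stable period: the last 3 months before entry.
- Window in which a drug change is compatible with entry: 12 − 3 = 9 months after the biopsy.
- Longest interval from entry biopsy to V2: 52 + 8 = 60 weeks, or 61 if counted from T-1. Only the last 8 weeks are step-1 exposure.

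**Effect on the primary count**

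- One child of 18 is 1/18 = 5.6 percentage points. Two are 2/18 = 11.1 and three are 3/18 = 16.7.
- A child who had already relapsed lowers the count only if he or she would otherwise have stayed in remission on step 1. The effect is therefore at most 5.6 points per such child, and always downward.
- The number of such children cannot be derived. The protocol does not say how many of the 18 will be on PPI or budesonide, how many will have had a change in the 9-month window, or how often such a change ends remission.

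**Biopsy age in general (assumed rates, a different quantity)**

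Suppose silent relapse runs at r = 5% to 20% a year in all 18 children, whether or not they take a drug, and the biopsy is m months old. The expected number already relapsed at V1 is 18 × (1 − (1 − r)^(m/12)).

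- m = 6: 18 × (1 − 0.95^0.5) = 0.46 to 18 × (1 − 0.80^0.5) = 1.90.
- m = 12 for every child (the extreme): 18 × 0.05 = 0.90 to 18 × 0.20 = 3.60.

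These figures describe ageing of the biopsy from any cause. They do not estimate the effect of drug changes.

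**Stopping rule (Statistical analysis)**

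The rule is: "If in all 18 children step 1 induces reoccurrence of the disease, the study will be stopped". Let p be true step-1 remission and q the share already relapsed. Then P(all 18 fail) = (1 − p(1 − q))^18. With assumed p = 0.30:

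- q = 0: 0.70^18 = 0.0016.
- q = 0.20: 1 − 0.30 × 0.80 = 0.76, and 0.76^18 = 0.007.

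Both probabilities are below 1%.

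**The case against.** The strongest reply is that the two limits control different things and do not contradict each other. Twelve months matches the yearly biopsies that the background describes for long-term PPI and spares children an extra endoscopy. Three months is longer than the 8 weeks after which the protocol judges histological response. This stands: the issue is a gap left between two reasonable limits, not an inconsistency.

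The second reply is the post-avoidance gastroscopy. It has real value. The drugs stay unchanged on study, so a relapse due to an earlier dose reduction would be expected to persist through avoidance, and persistence points away from the food. But no rule applies this result to the step-1 classification, and a transient cause that resolves during avoidance would still look food-related. Bringing the gastroscopy forward when symptoms appear, and excluding active disease, do not catch silent disease.

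Third, reporting is mainly descriptive with no testing, and tabulation by biopsy age could be left to an analysis plan. That is fair for the tabulation. It does not apply to eligibility, which the protocol itself fixes.

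Two stronger readings are tempting, and the documents do not support either. A reader might infer that false failures could stop the trial. The rule needs all 18 children to relapse, so a single remission prevents it, and the probabilities above hardly move unless true remission is already close to zero. A reader might also take 0.5 to 3.6 children as the size of the drug-change problem. Those figures rest on assumed rates applied to all children, on drugs or not, and the upper end places everyone at the maximum biopsy age despite the stated preference for a recent one.

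**Conclusion.** The point holds as a gap in eligibility. A child can enter with no biopsy on the current PPI or budesonide regimen, and remission lost before V1 would be recorded as a step-1 failure. The bias runs one way, towards understating remission on heated food, by 5.6 points for each child wrongly counted.

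The total size is unknown, because the documents give neither the number of children with drug changes nor a relapse rate. It could be nil if every child is enrolled soon after biopsy on an unchanged regimen, which the protocol prefers but does not require. The conclusion rests on the visit list being complete, with no gastroscopy at V0 or V1 for a child whose biopsy is within 12 months. The problem sits at step 1, since later steps start from the biopsy that ended the step before.

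It is worth correcting because the correction is cheap, not because the trial's result is shown to be wrong.

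**What to change.** 1. **Eligibility wording.** Require that background PPI or budesonide be unchanged since the qualifying biopsy, as well as for at least 3 months.
2. **Biopsy age.** Record the interval from the qualifying biopsy to V1 and list each child's step-1 result against it. With 18 children a listing is better than a split at an arbitrary cut-off. It also shows relapse on an unchanged regimen, which the eligibility wording does not address.
3. **Step-1 losses.** Report each one together with the post-avoidance biopsy, and mark those that persist after avoidance as not clearly attributable to the food. The primary count stays as defined, with the marked cases shown beside it.

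The cost is one phrase in the inclusion criterion and two descriptive listings, mostly from data already collected. No gastroscopy is added and no child's treatment is altered. Children whose drugs changed after their biopsy would enter after their next routine biopsy, which could mean a wait of up to about a year under yearly biopsies and could slow recruitment at a single centre. The listings remain descriptive and cannot establish cause in an individual child.

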The objective of the study is to study whether the introduction of heated food products (more specifically heated hen's egg and/or cow's milk) in children with EoE would be possible without re-occurrence of the eosinophilic inflammation, while the intake of less heated products might cause disease recidive. Moreover, we would like to study whether the gradual re-introduction of less heated products after the most heated form is tolerated, could lead to tolerance induction in EoE.

Primary end-point:

- Primary end-point of the study is to study the number of ped EoE children by inclusion on hen's egg and/or cow's milk free diet with potential remaining remission (<15 eosinophils/hpf on esophageal biopsies) after 8 weeks (re)introduction of heat-denatured hen's egg and/or cow's milk proteins (introduced sequentially as on the one hand baked egg (cake), hard-boiled egg, omelet and soft-boiled egg and on the other hand 20' cooked cow's milk, 15', 10' and 5' cooked cow's milk).

Secondary end-points:

- The number of pedEoE children in whom remission remain with introduction of cake and/or 20'cooked cow's milk (step 1), but no longer with less heated proteins
- To study whether remission is associated with specific circulating and/or local food protein IgG4 reduction (when baseline levels (serum) would be (stored) available) (and increase upon unsuccessful introduction of less heated proteins)
- To study whether remission could be associated with changes in local IgG4 production (on biopsy staining)
- To study whether we could develop an *in vitro* mimicking B cell activation test by stimulating PBMC with food proteins obtained after different heat-denaturating steps
- Can we observe a correlation between Pediatric EoE PEES v2.0 and Peds-QL scores (obtained in all ped EoE children participating in study s64441) and histologic remission?
- To study the presence of associated atopy (tree-, grass- or weed pollen or fungi allergy)
- To study the presence of associated typical IgE mediated food allergy (sensitization and documented symptoms)

Material and methods

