If remission remains, subjects will be invited to introduce 10' hard-boiled egg (consecutively hard-boiled egg white; hard-boiled egg yolk) or 15'boiled cow's milk at home (2-3 times a week) for 8 weeks, after which they will return to the hospital for the second gastroscopy with similar procedure.

If remission is lost, they will return to the strict avoidance diet for at least 10 weeks (allowing 2 weeks of additional healing) after which they will return to the hospital for their second gastroscopy. Upon remission after avoidance, the children will remain eligible for a second heat denatured food challenge (when on diet for both). When they are not on diet for both hen's egg and cow's milk, the study for them will end (final visit).

In children in whom remission remained after introduction of either hard-boiled egg or 15'boiled cow's milk, regular intake of 7' baked omelet or equivalent (waffle, pancake) or 10'boiled cow's milk will be introduced for 8 weeks after which they will return to the hospital for gastroscopy. Similarly as above, subjects will return to complete avoidance or (upon parental decision in agreement with treating physicians) they can return to introduction of the tolerated step (step 1) for 10 weeks, after which a new gastroscopy will be performed. When they are not on diet for both hen's egg and cow's milk, the study for them will end (final visit).

Similarly as above introduction of step 4, 4' soft-boiled egg or 5' boiled cow's milk will be introduced at home for 8 weeks afterwards upon remaining remission. Gastroscopy with biopsies is planned afterwards. If introduction of step 3 (omelet or 10' boiled cow's milk) was no longer associated with remission, children will return to complete avoidance or (upon parental decision together with treating physician) to step 1 or step 1+2.

Children who were able to tolerate step 4 for either hen's egg or cow's milk, will then be offered the possibility to choose for either termination of the study or (optionally) introduce either raw egg (tiramisu or chocolate mousse) or uncooked UHT-treated cow's milk for 8 weeks after which gastroscopy with biopsies will be performed.

For all steps if symptoms would (re)occur, gastroscopy with biopsy will be planned earlier and the introduction of the step will be on hold, until the biopsy would have proven remaining of remission. Upon EoE recidive, the patient will return to complete avoidance.

Number of study visits (n=9+4 telephone visits):

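### The protocol specifies no record of home intake, so a child who eats little of the study food is likely to be counted as keeping remission

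*Protocol*

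**What the plan says.** **Entry state.** The inclusion criterion admits children who eliminate hen's egg, cow's milk or both and are "in complete remission after their latest biopsy". The sample is fixed there too: "We will include 18 pedEoE subjects in total". There is one group and no control.

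**Primary end-point** (Study objectives). It is the number of children "with potential remaining remission (<15 eosinophils/hpf on esophageal biopsies) after 8 weeks (re)introduction" of the heated food. No amount or frequency of intake is part of the definition.

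**Exposure** (Study subjects and study procedure). One provocation in hospital opens step 1. After that:
- step 1 is to be eaten "at least three times a week for 8 weeks (as for the TETI study (10";
- step 2 reads "15'boiled cow's milk at home (2-3 times a week) for 8 weeks", with hard-boiled egg as the alternative;
- step 3 reads "regular intake of 7' baked omelet or equivalent (waffle, pancake) or 10'boiled cow's milk will be introduced for 8 weeks", with no number;
- step 4 is eaten at home for 8 weeks, with no frequency restated.

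**Contacts** (Number of study visits). Step 1 starts at V1, and the next listed contact is "T8 V2: 8 weeks later visit 2: gastroscopy with biopsy and biomarker". A telephone call about the biopsy result follows each gastroscopy from V2 to V8. V3, V5 and V7 consist of a clinical examination and dietary advice for the coming step. No item mentions reviewing what was eaten in the step just finished.

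**Adherence.** It appears in the study procedures only as an entry exclusion for children unwilling to follow the protocol. The (e)CRF content described under Adverse Event Reporting concerns adverse events.

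**The concern.** In most single-arm trials an untreated participant tends to look like a failure. Here it is the reverse: success is no change from the state at entry, and that state was reached by avoiding the food. A child who refuses or skips it is in effect still on the avoidance diet and will probably show fewer than 15 eosinophils/hpf at the next biopsy. That result adds to the primary count and passes the go/no-go call to a less heated step.

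The consequences go beyond the primary count. The secondary end-point on children who keep remission at step 1 but lose it with less heated food, and the IgG4 associations with remission, use the same classification. Under-eating is plausible on the protocol's own account: children from 12 months are eligible, feeding difficulties are listed among the common symptoms in younger children, and these patients have been taught to avoid the foods for life.

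An analysis plan cannot repair this later, because it cannot recover intake data that were never collected.

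**Working it through.** **1. Is intake recorded anywhere in the text shown?** The visit list gives four home periods, each running from the start of a step to its gastroscopy: weeks 0 to 8, 9 to 17, 18 to 26 and 27 to 35. No contact is listed inside any of them. The visits and calls around them cover provocation, gastroscopy, biomarkers, examination, advice for the next step and biopsy results. No diary, intake count, recall or minimum exposure is stated.

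**2. Is there a figure to reproduce?** No. The protocol gives no expected remission rate, no derivation of 18 and no non-intake rate; the Statistical analysis section foresees descriptive reporting without testing. What follows is illustration, not reproduction.

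**3. Model.** Let t be the true remission probability in children who eat the food, a the share who barely eat it, and r the remission probability of those who do not.

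Observed rate = t(1 − a) + a·r

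Expected extra successes = 18 × a × (r − t), taking all 18 as biopsied at step 1.

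The bias is upward whenever r is greater than t.

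**4. Inputs.** 18 comes from the protocol. The values of t (0.3, 0.5, 0.7), a (0.1 to 0.3) and r (1.0, then 0.9) are assumptions; none is in the documents.

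**5. Results with r = 1.0.**

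| True t | a = 0.1 | a = 0.3 | Extra successes in 18 |
|---|---|---|---|
| 0.3 | 0.27 + 0.10 = 0.37 | 0.21 + 0.30 = 0.51 | 1.26 to 3.78 |
| 0.5 | 0.45 + 0.10 = 0.55 | 0.35 + 0.30 = 0.65 | 0.90 to 2.70 |
| 0.7 | 0.63 + 0.10 = 0.73 | 0.49 + 0.30 = 0.79 | 0.54 to 1.62 |

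The smallest excess is 18 × 0.1 × 0.3 = 0.54 and the largest 18 × 0.3 × 0.7 = 3.78.

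**6. Softer assumption, r = 0.9.** A true 30% is seen as 0.27 + 0.09 = 36% to 0.21 + 0.27 = 48%, 50% as 54-62%, and 70% as 72-76%. The excess runs from 18 × 0.1 × 0.2 = 0.36 to 18 × 0.3 × 0.6 = 3.24 children. The direction is unchanged and the size slightly smaller.

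**7. Where could an intake criterion be applied now?** Step 1 implies 3 × 8 = 24 occasions as a minimum. Step 2 gives a range, 2 × 8 = 16 to 3 × 8 = 24. Steps 3 and 4 give no number, so no criterion can be derived from the text there.

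**The case against.** Several stronger readings are tempting, and the documents do not support them.

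- **That intake is never recorded.** The visit figure and one passage are not available, the provocation follows a separate written procedure that is not shown, and V3, V5 and V7 are face-to-face dietary visits at which intake could be discussed. The text supports only that no recording is specified.
- **That under-eating always produces a success.** The protocol itself names aeroallergens as a cause of disease activity and the pollen season as a time of raised oesophageal eosinophils. The entry biopsy may be up to 12 months old. A child who eats nothing can still have lost remission.
- **That every biopsy falls at a fixed week.** If symptoms occur, the gastroscopy is brought forward and the step is put on hold, so some children are biopsied after a shorter exposure.
- **That the stopping rule is defeated.** The study stops only if all 18 children relapse at step 1. At a non-intake share of 10% the chance of at least one non-eater is 1 − 0.9^18 = 85%, and at 5% it is 60%. These are chances of blocking a stop only if remission in true eaters is 0% and every non-eater stays in remission.

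Two further objections have force. The 10-30% range is invented, and the protocol leans somewhat against high refusal: it excludes children unwilling to adhere and expects families to value the food. And this is a small descriptive pilot in which a child wrongly advanced is biopsied again after each further step.

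A strict success rule of 24 occasions would also introduce faults of its own. It would test intake only in remissions, leave the denominator unclear, and discard a child over one missed portion.

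What remains is that no recording of intake is specified and that success equals the entry state. The descriptive nature of the study does not help, since the descriptive count is itself what is likely to be inflated.

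**Conclusion.** The point holds in a limited form. As written, the plan counts a child with little or no exposure in the same way as a child who ate the food and kept remission, and the data specified for collection could not tell the two apart. The likely bias is upward, provided children who do not eat the food keep remission more often than those who do; there is no control arm to reveal it.

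The documents do not give its size. Over the assumed range it is between about half a child and just under four children in 18. That is small if intake is good, and enough to change the reading of the pilot if it is not. The change is worth making before enrolment proceeds because it concerns data collection. It does not show that the trial's result would be wrong.

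**What to change.** 1. Add a parent-kept diary for every step (date and form of food eaten), collected at each gastroscopy visit, including gastroscopies brought forward because of symptoms.
2. Report the remission count among all children biopsied at each step, with its denominator.
3. Beside it, report the count and denominator among children whose diary meets the intake the protocol itself states for that step. Apply the same criterion to remissions and relapses, with a tolerance for isolated missed portions fixed in advance.
4. Show children put on hold and biopsied early separately, with their recorded exposure.
5. The sponsor must reconcile the intake wording across steps 1 to 4 before a criterion is applied at steps 3 and 4. Until then, report recorded intake there descriptively.

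Cost: a one-page form, a sentence or two in the protocol, a small burden on parents and possibly a slightly lower success count in the intake-restricted result. The sample size stays at 18, and no visit or procedure is added.
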